7.3 Labelling

Labels will be prepared in accordance with Good Manufacturing Practice (GMP) and local regulatory guidelines. The labels will fulfill GMP Annex 13 requirements for labelling. Label text will be translated into local language.

The label will include the following information:

1. Pharmaceutical dosage form, route of administration, and quantity of dosage units
2. Code number to identify the contents and packaging operation
3. Study code
4. Enrollment code (to be added on the label when IP is dispensed)
5. Directions for use
6. “For clinical trial use only”
7. Storage conditions
8. Period of use, e.g., expiration date
9. “Keep out of the reach of children”
10. The name of the Investigator, where applicable (to be added on the label when IP is dispensed)
11. Randomization code

7.4 Storage

All study drugs should be kept in a secure place under appropriate storage conditions. The IP label on the bottle specifies the appropriate storage.

7.5 Compliance

The patient will be asked about compliance at each study visit. Patients judged to be noncompliant (defined as taking less than 80% or more than 120% of the prescribed dose of IP) may continue in the study, but should be counseled on the importance of taking their study medication and applicable ancillary medications as prescribed.

The administration of all study medications (including IPs) should be recorded in the appropriate sections of the patient’s source records.

7.6 Accountability

The study drug provided for this study will be used as directed in the Study Protocol.

The study personnel will account for all study drugs dispensed and returned from the patient.

Study site personnel will account for all study medications received at the site, unused study medications and for appropriate destruction. Certificates of delivery, destruction, and return should be signed.

A drug disposition form will be used to record all study medication dispensed to or returned from each patient. Upon completion of the study, all unused study medication will be destroyed.

The study site personnel will maintain documentation of any missing, damaged, or unreturned study medication.

7.7 Concomitant and other treatments

Patients must follow the medication restrictions outlined in the inclusion and exclusion criteria during the study. Dosages for certain concomitant medications should be maintained constant during the study, unless instructed otherwise by the Investigator. Concomitant herbal or nutritional therapies will be recorded.

The table below lists prohibited medications and the applicable time frames.

Restricted Medication/Class of drug:	Usage
Cytochrome P450 3A4/5 inhibitors (e.g., atazanavir, clarithromycin, indinavir, itraconazole, nefazodone, nelfinavir, ritonavir, saquinavir, and telithromycin)	Prohibited during the study.
Other investigational drugs or participation in any interventional clinical study	Prohibited within 30 days prior to Visit 1 (Screening) and during the study.
Antihyperglycemic therapy	Administration of any antihyperglycemic therapy, other than metformin or sulfonylurea, for more than 14 days (consecutive or not) during the 12 weeks prior to Visit 1 (Screening) and during the study unless per protocol for rescue.
Systemic corticosteroids	Prohibited within 3 months prior to Visit 1 (Screening) and during the study.
Prescription or over-the-counter weight loss medications	Prohibited within 3 months prior to Visit 1 (Screening) and during the study.

7.7.1 Metformin/Sulfonylurea

Up to Visit 8 (Week 16), patients should continue to administer the same type and dose of metformin or metformin/sulfonylurea therapy they were using at study entry.

Neither metformin nor sulfonylurea will not be provided by the Investigator.

7.7.2 Rescue therapy

Patients must first complete a glucose turnover study and all Week 16 visit procedures, including OGTT, before receiving open-label rescue therapy. Patients who require rescue therapy (i.e., FPG rescue criteria met) should receive standard of care treatment; however, Bydureon 2 mg subcutaneously is highly suggested. Patients should continue receiving study medication while receiving rescue therapy. Bydureon will be provided by the Sponsor.

If rescue therapy fails, further therapy will be given at the discretion of the Investigator.

7.7.3 Other concomitant treatment

Other medication other than that described above, which is considered necessary for the patient's safety and well-being, may be given at the discretion of the Investigator and recorded in the source documents.

8. STATISTICAL ANALYSES

8.1 Statistical considerations

All personnel involved with the analysis of the study will remain blinded until database lock and protocol violators identified at the end of the 16-week randomized treatment period.

The primary efficacy measure of EGP will be derived by the Investigator. The remaining statistical analysis of this study will be performed by the Investigator.

Baseline: Unless otherwise specified, baseline refers to the last measurement collected prior to the first dose of study medication at the Randomization Visit. For parameters derived from the glucose turnover study and OGTT, several time points prior to the first dose of study medication may be averaged to calculate baseline.

All collected data will be listed. A comprehensive Statistical Analysis Plan (SAP) is described in the following sections.

8.2 Sample size estimate

This study will randomize patients to the following treatment arms (while continuing on metformin therapy):

- saxagliptin 5 mg + dapagliflozin 10 mg (n=21)
- dapagliflozin 10 mg + placebo for saxagliptin (n=21)
- placebo for dapagliflozin + placebo for saxagliptin (n=11).

The primary endpoint will compare the change in baseline EGP for saxagliptin (5 mg) plus dapagliflozin (10 mg) versus dapagliflozin (10 mg) at Week 16.

With 19 subjects per treatment group, there will be 90% power to detect a difference in mean EGP of 0.39 mg/kg/min between saxagliptin 5 mg plus dapagliflozin 10 mg and dapagliflozin 10 mg groups assuming a standard deviation of 0.32 using a 2 group t-test with a 0.050 2-sided significance level. Assuming that 10% of subjects in the primary comparison arms early terminate, are rescued, or do not have a Week 16 assessment for any other reason, a total of 21 subjects per treatment arm need to be randomized for each of the saxagliptin 5 mg plus dapagliflozin 10 mg and dapagliflozin 10 mg treatment arms. Approximately 11 subjects will be randomized to the placebo treatment arm for exploratory comparisons of saxagliptin 5 mg

plus dapagliflozin 10 mg to placebo (approximately 80% power), for a total of approximately 53 subjects randomized.

Assuming that 70% of screened patients will fail to meet screening criteria, a total of 177 patients will need to be screened.

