With 19 patients per treatment group, there will be 90% power to detect a difference in mean EGP of 0.39 mg/kg/min between saxagliptin 5 mg plus dapagliflozin 10 mg and dapagliflozin 10 mg groups assuming a standard deviation of 0.32 using a 2 group t-test with a 0.050 2-sided significance level. Assuming that 10% of subjects in the primary comparison arms early terminate, are rescued, or do not have a Week 16 assessment for any other reason, a total of 21 subjects per treatment arm need to be randomized for each of the saxagliptin 5 mg plus dapagliflozin 10 mg and dapagliflozin 10 mg treatment arms. Approximately 11 subjects will be randomized to the placebo treatment arm for exploratory comparisons of saxagliptin 5 mg plus dapagliflozin 10 mg to placebo (approximately 80% power), for a total of approximately 53 subjects randomized.

Assuming that 70% of screened subjects will fail to meet screening criteria, a total of 177 subjects will need to be screened.

Statistical considerations

Analysis populations:

Classification into Full analysis (FA), Per protocol (PP), and Safety analysis sets will be conducted prior to the database lock.

Primary analyses of efficacy endpoints (primary and secondary) will be performed on the FA set. Supportive analyses will be carried out with the PP analysis set if more than 10% of patients from the FA set are excluded from the PP analysis set for important protocol deviations. All safety analyses will be based on the Safety analysis set.

Efficacy analysis set

Full analysis set

The FA set will be defined as all randomized patients with a baseline and a post baseline efficacy assessment value. Patients will be analyzed according to the treatment assigned.

Per protocol analysis set

The PP analysis set will be defined as all FA patients without an important protocol deviation that might affect the primary analyses. The criteria for important protocol deviations will be defined in the statistical analysis plan. Patients will be analyzed according to the treatment randomized/received.

Safety analysis set

The Safety analysis set will be defined as all randomized patients who received at least 1 dose of study medication. Patients will be analyzed according to the actual treatment randomized/received.

Analysis of the primary variable:

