2. STUDY OBJECTIVES

2.1 Primary objective

Primary Objective:	Outcome Measure:
To compare the post-IP minus pre-IP endogenous glucose production (EGP) during the glucose turnover study in saxagliptin 5 mg plus dapagliflozin 10 mg vs dapagliflozin at Week 15.	
 Post-IP minus pre-IP EGP (mg/kg/min) during the glucose turnover study at Week 15.

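### The stated 90% power does not follow from its own inputs: 19 per arm, difference 0.39, SD 0.32 and a two-sided 0.05 t-test give about 95.5%, and 16 per arm would already exceed 90%

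*Combined protocol and SAP*

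**What the plan says.** Section 8.2 (Sample size estimate) gives a complete specification for the primary comparison: "With 19 subjects per treatment group, there will be 90% power to detect a difference in mean EGP of 0.39 mg/kg/min" between saxagliptin plus dapagliflozin and dapagliflozin alone, "assuming a standard deviation of 0.32 using a 2 group t-test with a 0.050 2-sided significance level". The sample size paragraph of the synopsis carries the same numbers: "With 19 patients per treatment group, there will be 90% power to detect a difference in mean EGP of 0.39 mg/kg/min". Both places then allow for 10% of patients not contributing and raise 19 to 21 randomised per arm, so 19 is the evaluable number before any loss.

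The significance level is consistent elsewhere. The synopsis (analysis of the primary variable) and section 8.5 both test the primary comparison at two-sided 0.05 and say that no multiplicity control is needed. Neither sample size paragraph gives a source for the difference or the SD.

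**The concern.** A power statement with n, difference, SD, test and significance level all given can be checked directly, and this one looked too low. The stated standardised difference is 0.39/0.32 = 1.22, which is large. A two-group t-test at two-sided 0.05 should need fewer than 19 per arm to detect it with 90% power.

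What is at stake is the accuracy of the design rationale, not the validity of the test. If 0.39 and 0.32 are the intended values, the trial is simply better powered than it says. If the intended difference was smaller or the SD larger, the protocol misdescribes what the trial was planned to detect and the apparent spare power does not exist. As written, a reader cannot tell whether 90% power applies to 0.39 or to something nearer 0.35.

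**Working it through.** **Inputs**, all from section 8.2 and repeated in the synopsis: n = 19 per arm, equal allocation; difference d = 0.39 mg/kg/min; SD s = 0.32; two-group t-test; two-sided significance level 0.05. Stated result: 90% power.

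**Method.** Exact power from the noncentral t distribution with 2n − 2 degrees of freedom and noncentrality d / (s × √(2/n)) = (d/s) × √(n/2). Power is the probability that |t| exceeds its two-sided 5% critical value.

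**Attempt to reproduce the plan's figure.** At n = 19 the noncentrality is 1.21875 × √9.5 = 3.756, with 36 degrees of freedom and critical value 2.028. Power is 95.5%, not 90%. The normal approximation gives a larger figure, 96.4%.

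**Power by n at the stated difference and SD:**

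| Evaluable per arm | Power |
|---|---|
| 15 | 89.6% |
| 16 | 91.5% |
| 18 | 94.4% |
| 19 (plan) | 95.5% |
| 21 (number randomised) | 97.1% |

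The smallest n that reaches 90% is 16. With the plan's 10% loss, 16/0.9 = 17.8, so 18 randomised per arm against the plan's 21 (36 against 42 over the two arms).

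**Rounding of the inputs, n = 19.** Difference 0.385 with SD 0.325 gives 94.4%. Difference 0.395 with SD 0.315 gives 96.4%. Rounding does not reach 90%.

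**What 90% at 19 per arm would imply.** Solving for the standardised difference gives 1.081, against 1.219 stated. Equivalent pairs:
- SD held at 0.32: difference 1.081 × 0.32 = 0.346
- difference held at 0.39: SD 0.39/1.081 = 0.361

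**Other settings that return 19 as the smallest n, with 0.39 and 0.32 unchanged:**
- 95% power at two-sided 0.05: n = 18 gives 94.4%, n = 19 gives 95.5%
- 90% power at two-sided 0.025: n = 18 gives 89.9%, n = 19 gives 91.7%

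The documents state neither setting. Each would mean that one printed figure, the power or the significance level, is wrong.

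**The case against.** The best defence is that the error is harmless. With the figures as printed, the trial has more power than claimed. Even if the real difference was nearer 0.35 or the real SD nearer 0.36, 19 per arm would still deliver 90%. A single misprint, 90% for 95%, explains the whole mismatch, so there is no positive evidence that the difference or SD is misdescribed. The primary analysis is also an ANCOVA reported with a 95% confidence interval. A null result would be read mainly from that interval, and the precision achieved would match neither 90% nor 95.5% exactly.

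Most of this stands as a limit on the point's weight. Nothing here biases the analysis or shows the trial to be underpowered, and the confidence interval will matter more than planned power once results exist. It does not make the statement correct. The text names a t-test, so the ANCOVA is not the basis of the calculation. The 10% loss is applied after 19, so it does not absorb the gap. The significance level is confirmed as two-sided 0.05 without multiplicity control, so an unstated 0.025 does not rescue the figure. That a misprinted power is the simplest explanation is plausible, but only the sponsor's source can confirm it.

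**Conclusion.** The concern holds. The stated inputs give 95.5% power at 19 per arm (94.4% to 96.4% allowing for rounding), 5.5 points above the stated 90%. For 90% they need 16 evaluable per arm, three fewer than planned. At 19 per arm and SD 0.32, the difference detectable with 90% power is 0.346, not 0.39.

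This rests only on the printed inputs and an equal-variance two-group t-test. Which of the difference, SD, n, power or significance level is misreported cannot be settled from the documents. The error is conservative if 0.39 and 0.32 are right. It is a correction the sponsor should make to the central planning statement, not a threat to the trial's validity.

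**What to change.** Leave the sample size and enrolment as they are. Check the sponsor's original calculation, then amend section 8.2 and the synopsis in the same way:
- if 0.39 and 0.32 are confirmed, state that 19 evaluable per arm gives about 95% power for 0.39, and 90% for about 0.35;
- if the source shows a different difference or SD, correct that input, cite the source and keep 90%;
- if the source shows a different significance level, state it and reconcile it with the two-sided 0.05 in section 8.5.

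Two clarifications could go into the same edit, although the finding does not depend on them. First, name the EGP quantity and visit that the difference and SD describe: section 8.2 refers to a change at Week 16, while section 2.1 defines the primary measure as "Post-IP minus pre-IP EGP (mg/kg/min) during the glucose turnover study at Week 15". Second, give the difference, SD and evaluable numbers behind the approximate 80% power for the exploratory comparison with placebo.

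The cost is one or two sentences in each place for the main correction, with no added patients or procedures.

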8.3 Definitions of analysis sets

Classification into Full analysis (FA), Per protocol (PP), and Safety sets will be conducted prior to the database lock.

Primary analyses of efficacy endpoints (primary and secondary) will be performed on the FA set. Supportive analyses will be carried out with the PP analysis set if more than 10% of patients from the FA set are excluded from the PP analysis set for important protocol deviations. All safety analyses will be based on the Safety set.

8.3.1 Efficacy analysis set

Full analysis set

- The FA set will be defined as all randomized patients with a baseline and a post baseline efficacy assessment value. Patients will be analyzed according to the treatment assigned.

Per protocol analysis set

- The PP analysis set will be defined as all FA patients without an important protocol deviation that might affect the primary analyses. The criteria for important protocol deviations will be defined in the SAP. Patients will be analyzed according to the treatment received.

Safety analysis set

- The Safety analysis set will be defined as all randomized patients who received at least 1 dose of study medication. Patients will be analyzed according to the actual treatment received.

8.4 Outcome measures for analyses

The mean values will be compared between the treatment groups for the following measures:

1. Post-IP minus pre-IP EGP during glucose turnover study at Week 15.
2. Post-IP minus pre-IP EGP during glucose turnover study at Week 0 and the change from Week 0 to Week 15.
3. Pre-IP EGP during glucose turnover study at Week 15 and the change from Week 0 to Week 15.

4. Pre-glucose load EGP during the OGTT at Week 16 and the change from Week -1 to Week 16.
5. Change from Week -1 to Week 16 in post-glucose load EGP during the OGTT.
6. Change from Week -1 to Week 16 in Rd and Ra during OGTT.
7. Change from Week 0 to Week 16 in HbA1c.
8. Change from Week 0 to Week 15 in pre-IP plasma glucose during glucose turnover study.
9. Change from Week -1 to Week 16 in pre-glucose load FPG and post-glucose load PPG during the glucose turnover study.
10. Change from Week -1/0 to Week 15/16 in fasting plasma glucagon, C-peptide, and insulin during the glucose turnover study and OGTT.
11. Change from Week -1/0 to Week 15/16 in plasma glucagon, C-peptide, and insulin during the glucose turnover study and OGTT.
12. Change from Week 0 to Week 15 in post-IP minus pre-IP plasma glucagon, C-peptide, and insulin during the glucose turnover study.
13. Change from Week -1 to Week 16 in insulin secretion, beta cell function, and insulin sensitivity during OGTT.
14. Change in glucose oxidation and lipid oxidation during the baseline of the glucose turnover study, during the baseline of the OGTT, and post-glucose load during the OGTT.
15. Change in plasma ketones during the baseline of the glucose turnover study and OGTT.
16. Change from Week 0 to Week 15 in pre-IP, post-IP, and post-IP minus pre-IP in counterregulatory hormones during glucose turnover study.
17. Change from Week -2 to Week 16 in body weight and BMI; and percent body fat and fat distribution calculated from the DEXA scans.
18. Change from Week -1 to Week 16 in plasma GLP-1, GIP, and FFA during OGTT.
19. Change from Week -2 to Week 16 in FFA.
20. Change from Week 0 to Week 16 in waist to hip ratio, BP, and lipids.

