To compare the mean change from Week 0 to Week 15 in post-IP minus pre-IP plasma glucagon, plasma C-peptide, and plasma insulin during glucose turnover study and post-glucose load (during OGTT) in saxagliptin plus dapagliflozin vs dapagliflozin.	
 • Change from Week 0 to Week 15 in post-IP minus pre-IP plasma glucagon (pg/mL), C-peptide (ng/mL), and insulin (μU/mL) during the glucose turnover study.

Secondary Objectives:	Outcome Measures:

To compare the mean change from Week -1 to Week 16 in insulin secretion, beta cell function, and insulin sensitivity during the OGTT in saxagliptin plus dapagliflozin vs dapagliflozin.
	
 • Change from Week -1 to Week 16 in insulin secretion (change in C-peptide or insulin and change in C-peptide or insulin/change in glucose, as mean and AUC). • Change from Week -1 to Week 16 in beta cell function (as change in C-peptide [ng/mL] or insulin/change in glucose [mg/dL] ÷ insulin resistance). • Change from Week -1 to Week 16 in insulin sensitivity (mg/kg·min per μU/mL).

To compare the mean change from Week 0 to Week 15 in pre-IP, post-IP, and post-IP minus pre-IP counterregulatory hormones during glucose turnover study achieved with saxagliptin plus dapagliflozin vs dapagliflozin.
	
 • Change from Week 0 to Week 15 in pre-IP cortisol (ng/mL). • Change from Week 0 to Week 15 in post-IP cortisol (ng/mL). • Change from Week 0 to Week 15 in post-IP minus pre-IP cortisol (ng/mL). • Change from Week 0 to Week 15 in pre-IP epinephrine, norepinephrine, and growth hormone (pg/mL). • Change from Week 0 to Week 15 in post-IP epinephrine, norepinephrine, and growth hormone (pg/mL). • Change from Week 0 to Week 15 in post-IP minus pre-IP epinephrine, norepinephrine, and growth hormone (pg/mL).

To compare the mean change from Week -2 to Week 16 in body weight, body mass index (BMI), percent body fat, and fat distribution in saxagliptin plus dapagliflozin vs dapagliflozin.
	
 • Change from Week -2 to Week 16 in body weight (kg). • Change from Week -2 to Week 16 in BMI. • Change from Week -2 to Week 16 in percent body fat and fat distribution (per Dual Energy X-ray Absorption [DEXA] scan).

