4.1.1 Screening Visit (Visit 1, Week -2)

At Screening, informed consent will be obtained prior to performing any protocol-required procedures. Patients will be assessed to ensure that they meet eligibility criteria. Patients who do not meet these criteria must not be enrolled in the study.

Screening procedures should be scheduled for at least 1 day later than the day of informed consent signature if the patient is not in a fasting state on the consent date.

The following will be performed during this visit:

- The patient's complete medical and surgical history will be recorded.
- Inclusion and exclusion criteria will be verified.
- A complete physical exam will be conducted.
- Body weight and height will be measured.
- BMI will be calculated.
- Vital signs (reclining and standing systolic and diastolic BP and heart rate [HR]) will be measured.
- Waist and hip circumference will be measured.
- 12-lead ECG will be performed.
- All prior medications (prescription medications within 3 months) and concomitant medications (including over the counter and herbal/nutritional supplements) will be reviewed.
- Diet and exercise counselling will be provided.
- Urinary pregnancy test for all female patients (WOCBP only) will be performed.
- Blood samples will be collected for the following assessments:
 - Chemistry and hematology
 - Serum creatinine (estimated GFR)
 - HbA1c
 - Fasting plasma glucose (FPG) and ketones

- Fasting serum lipid concentrations (total cholesterol, low-density lipoprotein [LDL] cholesterol, high-density lipoprotein [HDL] cholesterol, non-HDL cholesterol, and triglycerides)
- Thyroid function (TSH and T4)
- FFA
- Serum pregnancy test for all female patients (WOCBP only) if urine pregnancy test result is positive
- Urine will be collected for urinalysis.
- DEXA scan will be performed.

Individuals will be screen failed if results of any laboratory test are abnormal and clinically significant as judged by the Investigator or medical monitor. Individuals may qualify for study run-in following an acceptable repeated lab result for an initially abnormal result as judged by the Investigator).

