4.1.3 Randomization and Baseline Visit (Visit 3, Week 0)

Visit 3 should take place 3 to 5 days after Visit 2. Prior to this visit, patients are to have fasted overnight (at least 10 hours). Patients are to refrain from alcohol intake and intense exercise 24 hours prior to each visit and recommend not to use tobacco/nicotine within 12 hours prior to each visit. Patients should delay administering their morning dose of metformin on the morning of the study site visit. The following will be performed during this visit:

- Randomization criteria will be verified.
- Body weight will be measured.
- Vital signs (sitting systolic and diastolic BP and HR) will be assessed.
- Waist and hip circumference will be measured.
- Concomitant medications (including over-the-counter and herbal/nutritional supplements) will be reviewed.
- Urinary pregnancy test for all female patients (WOCBP only) will be performed.
- Patients will perform 7-point SMBG prior to the visit.

- AEs will be reviewed.
- Blood samples will be collected **prior to glucose turnover study and administration of study medication** for the following assessments:
 - FPG and ketones
 - Serum pregnancy test for all female patients (WOCBP only) if urine pregnancy test result is positive
- Glucose turnover study will be initiated.
- During the baseline infusion period of the glucose turnover study, prior to Time 0 collection, the following will be performed:
 - Diet and exercise counselling will be provided.
 - 7-point SMBG will be reviewed and recorded.
 - Patients will be randomly assigned to 1 of 3 treatment groups (while continuing on metformin therapy):
 - saxagliptin 5 mg + dapagliflozin 10 mg;
 - dapagliflozin 10 mg + placebo for saxagliptin;
 - placebo for dapagliflozin + placebo for saxagliptin.
 - Study medication will be dispensed during Time 0 of glucose turnover study. Study site personnel will monitor administration of study medication. Glucose turnover study will be completed.

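### Weight and BMI change starts at Week -2 although a Week 0 weight is scheduled, so the within-arm changes include nominally two pre-drug weeks

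*Combined protocol and SAP*

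**What the plan says.** Section 8.4, item 17, puts four measures on one interval: it begins "Change from Week -2 to Week 16 in body weight and BMI" and adds the two DEXA measures. Section 2.2 has the matching objective, "To compare the mean change from Week -2 to Week 16 in body weight, body mass index (BMI), percent body fat, and fat distribution", and the synopsis uses the same weeks.

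The general rule in section 8.1 is: "Unless otherwise specified, baseline refers to the last measurement collected prior to the first dose of study medication at the Randomization Visit".

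The schedule (Table 1 and sections 4.1.1, 4.1.3 and 5.1.7) is as follows:
- **Weight:** Visit 1 and Visits 3 to 8. For Visit 3, section 4.1.3 states "Body weight will be measured", listed ahead of the turnover study in which the first dose is given at Time 0.
- **BMI:** Visits 1 and 8. Height is taken at Visit 1 only.
- **DEXA:** Visits 1 and 8 only.
- **Counselling:** at Visit 1, "Diet and exercise counselling will be provided"; it is repeated at Visits 3 and 5.

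Section 8.5.2 reports adjusted mean changes with 95% confidence intervals within each arm, as well as differences between arms.

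**The concern.** The weight change score starts at a visit where patients are counselled on diet and exercise, two nominal weeks before any study drug. A later weight, at the visit where drug starts, is already planned. Any weight change between the two visits enters each arm's reported change, and a reader will naturally take that figure as change on treatment.

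The plan gives no reason for this start point. Waist and hip circumference and blood pressure are, like weight, measured at both Visit 1 and Visit 3, yet item 20 of section 8.4 takes their change from Week 0. Section 8.5.2 also calls Visit 3 the baseline visit. Of the measures in item 17, only the DEXA results have no possible Week 0 value.

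At stake are the interpretation of the within-arm changes and some precision in the comparison between arms.

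**Working it through.** The documents give no SD, effect size or power for weight or BMI (section 8.2 covers EGP only), so there is no stated figure to reproduce. Every kilogram value below is an assumption. Item 17 does not say separately which weight is the model covariate; I take it to be the Week -2 value.

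**1. Length of the pre-drug part.** In Table 1, Visit 1 is Day -14, randomization is Day 0 and Visit 8 is Day 112.
- Nominal: 14 / (14 + 112) = 14/126 = 11.1%.
- If the +7 day window moves Visit 1 to Day -7: 7 / (7 + 112) = 7/119 = 5.9%.

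**2. What the change score contains.** With W for weight:

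W16 - W(-2) = (W16 - W0) + (W0 - W(-2))

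The last term is run-in change. It enters each within-arm mean in full. For illustration, an average run-in loss of 0.3 to 1.0 kg would overstate each arm's on-drug loss by 0.3 to 1.0 kg; a run-in gain would understate it.

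**3. Difference between arms.** Randomization is at Week 0, so run-in change has the same expectation in every arm and cancels. An ANCOVA simulation (19 per arm, 4,000 runs per scenario) agrees. Its assumptions were: weight SD 18 kg; on-treatment change SD 2.5 kg; control change -2 kg; true difference -1 kg; run-in mean 0, -0.5 or -1.0 kg; run-in SD 0.5, 1.0 or 1.5 kg; run-in independent of on-treatment change.
- Estimated difference: -0.99 to -1.01 kg from either baseline, in every scenario.
- Arm mean changes with a run-in mean of -1.0 kg: control -3.0 kg from Week -2 against -2.0 kg from Week 0; treated -4.0 against -3.0 kg.

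**4. Precision.** Let s be the SD of run-in change, and let the SD of W16 - W0 be 3 kg.

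SE ratio = sqrt[(9 + s² + 2·cov) / 9], where cov is the covariance of the two terms in step 2.
- Independent (cov = 0), s = 0.7: sqrt(1 + 0.49/9) = 1.027.
- Independent, s = 1.0: sqrt(1 + 1/9) = 1.054.
- Run-in change is pure fluctuation with variance e² at each weighing: s² = 2e² and cov = -e², because W0 appears in both terms with opposite sign. For s = 0.7, e² = 0.245 and the numerator is 9 + 0.49 - 2(0.245) = 9, so the ratio is 1.000. The same holds for s = 1.0.

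The range is therefore about 0% to 5%. The result depends on the assumed SDs: under the simulation's inputs (on-treatment SD 2.5 kg, independence), the standard error falls from about 0.82 to 0.80 kg at a run-in SD of 0.5, from 0.89 to 0.82 at 1.0, and from 0.97 to 0.83 at 1.5.

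**The case against.** There are four arguments for leaving the text alone.

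- **The start point is permitted and consistent.** Section 8.1 opens with an exception clause, item 17 uses it, and the synopsis, 2.2 and 8.4 agree. This stands. A reader might infer that item 17 contradicts section 8.1; it does not.
- **The treatment comparison is not biased.** A reader might infer that two weeks of pre-drug weight loss are being credited to the drug. The documents do not support this. The objective compares randomized arms and randomization follows the run-in, so the run-in change cancels in expectation. It also cancels in the exploratory comparisons with placebo. This stands, and it confines the point to within-arm figures and precision.
- **A common interval has a use.** BMI and DEXA are scheduled only at Visits 1 and 8, so one start point lets weight loss and fat loss be read together. This stands in part. BMI at Week 0 can be derived from Visit 3 weight and screening height, but DEXA cannot be moved, so changing weight does separate the two.
- **A within-arm change is not a drug effect from either baseline.** Counselling is repeated at Visits 3 and 5, so a Week 0 start still mixes counselling with drug. This is true. A Week 0 start nevertheless removes the interval when no drug was taken, and the plan reports these figures with confidence intervals.

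**Conclusion.** The point holds as a minor improvement on an unpowered secondary endpoint. The within-arm adjusted changes in weight and BMI will include nominally two pre-drug weeks (about one if the window is used), equal in size to whatever the run-in change proves to be; the documents give no basis for its size or direction. The randomized difference is unbiased. Its standard error may be about 0% to 5% larger under the assumed SDs (0.7 to 1.0 kg over two weeks, 3 kg over 16 weeks). The lower end applies if run-in change is only day-to-day fluctuation, and the upper end needs it to be independent of later change. Nothing here affects the primary EGP analysis.

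**What to change.** In the synopsis, section 2.2 and section 8.4 item 17 together:
- Define weight and BMI change from Week 0 to Week 16, using the Visit 3 weight, and screening height for BMI.
- State that the Visit 3 weight is taken before the Time 0 dose. Section 4.1.3 implies this by its order but does not say so.
- In section 8.5.2, name that value as the baseline covariate. This also settles whether the Week 0 weight is a modelled visit in the repeated measures analysis, which the plan leaves open.
- Keep Week -2 to Week 16 for the DEXA measures only.

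The cost is wording; no visit or measurement is added. The small downside is that weight and DEXA changes will cover slightly different intervals. If a common interval is wanted, the change in weight from Week -2 can be listed beside the DEXA results as a descriptive figure. The synopsis must be edited with the other two places, or the change would create an inconsistency that does not exist now.
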